5.1.1. Visit Windows

5.1.1.1. Visit Windows for Dosing and PK Analysis

All post-baseline visits from Baseline through Week 16 will have a visit window of ± 7 days counting from week 0 as Day 1. If a study visit occurs outside this window, the Sponsor should be consulted about how the participant should resume his or her normal dose schedule.

For PK analyses, if a participant has an administration outside the visit window at a visit, the concentration data collected at and after that visit will be excluded from the by-visit data analyses.

Information regarding study intervention administrations that are administered outside of the scheduled windows or missed will be recorded. Participant charts and worksheets may be reviewed and compared with the data entries on the eCRFs to ensure accuracy.

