Hepatitis B and C serology l	X															
HIV Ab test	X															
Hematology	X	X	X		X	X		X		X				X	X	X
Chemistry	X	X	X		X	X		X		X				X	X	X
Lipid panel n		X						X						X	X	X
Hs-CRP		X	X			X		X		X				X	X	X
HbA1c		X						X						X	X	X

Phase	Screening a	Placebo b				Active Treatment b								Follow-Up b,c		
Week		0	4	8	12	16	20	24	28	32	36	40	44 (last dose)	48 (Final Efficacy)	Early Term.	56 (Final Safety)
Clinical Pharmacology and Biomarker Assessments p																
Serum guselkumab concentration		X	X			X				X				X	X	X
Anti-guselkumab antibodies		X	X			X				X				X	X	X
Serum biomarkers		X	X			X				X				X		
Optional Substudies e																
Skin biopsy p		X				X								X		
Tape stripping		X	X			X				X				X		
Whole blood (pharmacogenomics) q		X														
Ongoing Participant Review																
Concomitant therapy	X	X	X	X	X	X	X	X	X	X	X	X	X	X	X	X
Adverse events	X	X	X	X	X	X	X	X	X	X	X	X	X	X	X	X

a: The screening visit should occur within approximately 4 weeks before the Week 0 visit.

b: All post-baseline visits will have a visit window of  $\pm 7$  days counting from Week 0 as Day 1.

c: If a participant permanently discontinues study drug intervention prior to the Week 16 visit, they should be encouraged to return for all remaining study visits through Week 16, and the participant should also return for a final visit to perform assessments under the Week 56/final safety visit approximately 12 weeks after the last study intervention administration. If a participant permanently discontinues study drug at or after the Week 16 visit, they should complete the Week 48/final efficacy visit assessments at the time of discontinuation, or as soon as possible, and also return for a final safety visit to perform assessments under the Week 56/final safety visit approximately 12 weeks after the last study intervention administration.

d: All study procedures and evaluations should be completed before administration of study drug.

e: ICFs must be signed before the first study-related activity. The optional skin biopsy, tape stripping, and pharmacogenomics substudies will use separate ICFs.

f: Details may be found in the Photography Manual.

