#### 6.4. Study Intervention Compliance

In this study, the **CC** investigational product (IP, guselkumab/placebo) will be administered at the study site.

Compliance will be assessed by direct questioning during the site visits and documented in the source documents and eCRF. Deviation(s) from the prescribed dosage regimen should be recorded in the eCRF.

During the study, the investigator or designated study research personnel will be responsible for providing additional instruction to reeducate any participant who is not compliant with taking the study intervention.

Compliance with the treatment schedule is strongly encouraged. It is understood that treatment may be interrupted for health-related or safety reasons.

- If, for any reason, a participant cannot receive the study intervention at the scheduled visit, the participant must make every effort to still come in for the scheduled assessments for that visit.
- In general, the dose should be administered within approximately 2 weeks of that scheduled visit.
- The participant should then resume the normal study schedule relative to the baseline visit (Week 0).

In the case when a participant does not come into the study site for a scheduled visit, the site will follow up with that participant. Due diligence could include telephone calls, certified letters, and email requests. Measures taken to obtain follow-up information must be documented.

- Study site personnel will keep a log of all study intervention dispensed and will compare the amount of study intervention dispensed with the amount returned.

All post-baseline visits will have a visit window of approximately  $\pm 7$  days counting from Week 0 as Day 1. If a study visit occurs outside this window, the Sponsor should be consulted about how the participant should resume his or her normal dose schedule.

Information regarding study intervention administrations that are administered outside of the scheduled windows or missed will be recorded. Participant charts and worksheets may be reviewed and compared with the data entries on the eCRFs to ensure accuracy.

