5.7. Other Analyses

5.7.1. Pharmacokinetics

Blood samples for measuring serum guselkumab concentrations will be collected from all participants at scheduled visits as indicated in the Schedule of Events in the protocol.

The PK analysis will be based on participants who received at least 1 administration of guselkumab and had at least one evaluable serum sample. No imputation of missing concentration data will be performed, that is, data summaries will be based on the observed data.

For analysis on serum guselkumab concentrations, descriptive statistics, including arithmetic mean, SD, median, interquartile range, minimum, and maximum will be provided, where appropriate, by treatment group at each serum sampling time. The PK concentration data may also be displayed graphically. The following analyses will be performed by treatment group as appropriate:

- Summary of serum guselkumab concentrations at each visit by treatment group

- Participants with serum guselkumab concentration below the lowest quantifiable concentration in a sample will be summarized by treatment group overtime.
- Summary of serum guselkumab concentrations overall and by baseline weight (≤ 90 kg, >90 kg) will be summarized by treatment group overtime.
- Plot of median serum guselkumab concentrations over time by treatment group

In addition, the relationship between serum guselkumab concentrations and safety or efficacy may be explored.

For summary statistics of serum guselkumab concentrations, concentration values below the lower limit of quantification will be treated as zero. Once a Participant meets one of the following dosing deviation criteria, the participant's data will be excluded from the by-visit data analyses from that point onwards.

Dosing deviation criteria:

- Discontinue ███ guselkumab administrations.
- Skipped an ███ guselkumab administration.
- Received an incomplete/ incorrect ███ dose.
- Received an incorrect ███ study agent.
- Received an additional ███ guselkumab dose.

In addition, if a participant has an administration outside of visit windows (Section 5.1.1), the concentration data collected at and after that visit will be excluded from the by-visit data analyses. Additional exclusions for incongruous PK data to be implemented based on Janssen SOP-07948.

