Population PK analyses will be performed to characterize the disposition characteristics of guselkumab based on the guselkumab concentration data from PSO studies. Data may be combined with other selected studies to support a relevant structural model. A detailed analysis plan for population PK analysis will be developed separately, and a stand-alone technical report will be written to summarize the results of the population PK analysis.

PK analyses presentation

PK analyses will be summarized through the following time periods:

- Through Week 16
- Through Week 48

For the analyses, a Participant is included in one and only one treatment group on the basis of the treatment regimen followed. The description of treatment groups are as follows:

1. **Placebo → Guselkumab** ███ ███ Participants randomized to placebo and were switched over to Guselkumab ███ ███ (due to CO) at Week 16.

2. **Guselkumab** [REDACTED] at Week 0, Week 4, and then [REDACTED] Participants randomized to guselkumab [REDACTED] at Week 0, Week 4, and then [REDACTED] and received guselkumab [REDACTED] [REDACTED] throughout.

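### The SAP's ±7-day window for excluding by-visit PK data stops at Week 16, while the protocol's window covers all post-baseline visits and dosing runs to Week 44

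*SAP*

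**What the plan says.** SAP 5.1.1.1, which sets windows for dosing and PK analysis, says "All post-baseline visits from Baseline through Week 16 will have a visit window" of ±7 days counted from Week 0 as Day 1. For an administration outside the window it says "the concentration data collected at and after that visit will be excluded from the by-visit data analyses". SAP 5.7.1 repeats the rule by cross-reference: "if a participant has an administration outside of visit windows (Section 5.1.1), the concentration data collected at and after that visit will be excluded". No other dosing window is given in the SAP.

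The protocol has no Week 16 limit. Schedule of Activities footnote b reads "All post-baseline visits will have a visit window of" ±7 days, and Section 6.4 reads "All post-baseline visits will have a visit window of approximately" ±7 days. Section 6.4 also covers a participant who cannot be dosed at a scheduled visit: "In general, the dose should be administered within approximately 2 weeks of that scheduled visit", after which the participant returns to the schedule counted from Week 0.

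On the reach of the analysis, SAP 5.7.1 says "PK analyses will be summarized through the following time periods" and lists Week 16 and Week 48. Crossover participants receive guselkumab at Weeks 16, 20, 28, 36 and 44.

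**The concern.** The by-visit exclusion exists so that concentrations shown at a nominal visit come from participants dosed close to schedule. With a window that ends at Week 16, the SAP supplies no test of lateness for the doses that determine the Week 32 and Week 48 samples. The same delay is therefore handled in opposite ways depending on when it occurs, and no reason is given.

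At stake is which participants enter the Week 32 and Week 48 concentration summaries, including the breakdown by baseline weight and, if it is done, the one by antibody status. If the text is left as it is, someone must choose after the data exist whether to follow the SAP wording or to borrow the protocol window.

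**Working it through.** The plan gives no figure to reproduce here. The check applies the rule dose by dose.

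**Inputs**
- Scheduled PK samples (Schedule of Activities): Weeks 0, 4, 16, 32, 48 and 56, plus early termination. Samples are taken before dosing. Week 56 lies beyond the through-Week-48 summary.
- Active doses, crossover group: Weeks 16, 20, 28, 36, 44 (stated).
- Active doses, guselkumab group: Weeks 0, 4, 12 (stated), then 20, 28, 36, 44 (inferred, because the interval is redacted).
- Delay examined: 8 to 14 days, which is outside ±7 days but within the approximately 2 weeks of protocol 6.4.

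**Rule.** If the late dose falls at a visit with a window, drop every scheduled sample at that visit or later. Otherwise drop none.

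| Late active dose | Group | Samples dropped, SAP as written | Samples dropped, protocol window |
|---|---|---|---|
| Week 4 | guselkumab | 4, 16, 32, 48, 56 | 4, 16, 32, 48, 56 |
| Week 12 | guselkumab | 16, 32, 48, 56 | 16, 32, 48, 56 |
| Week 16 | crossover | 16, 32, 48, 56 | 16, 32, 48, 56 |
| Week 20 or 28 | both | none | 32, 48, 56 |
| Week 36 or 44 | both | none | 48, 56 |

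**Doses without a SAP window.** Guselkumab group: 4 of 6 post-baseline active doses (20, 28, 36, 44 out of 4, 12, 20, 28, 36, 44). Crossover group: 4 of 5.

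**Effect on sample timing.** Week w falls on Day 7w + 1.
- Week 28 is Day 197. A dose 14 days late is given on Day 197 + 14 = Day 211.
- Week 32 is Day 225, and stays there because the schedule is counted from Week 0.
- The sample is then 225 − 211 = 14 days after the dose, instead of 225 − 197 = 28. The Week 44 dose and the Week 48 sample behave in the same way.

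**Do other SAP criteria catch this case?** The dosing-deviation list in SAP 5.7.1 covers discontinued, skipped, incomplete or incorrect, wrong-agent and additional doses. A complete, correct dose given late is none of these.

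**Where the two readings differ.** They agree for every late dose through Week 16, so the through-Week-16 summary does not change. They differ only for Weeks 32 and 48 within the through-Week-48 summary. For the crossover group these are the only scheduled samples on guselkumab in that summary, because its Week 16 sample precedes the first guselkumab dose.

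**The case against.** The best defence is that the SAP never says late doses after Week 16 are kept. It is silent, the protocol supplies a ±7-day window for all visits, and an analyst could use that. SAP 5.7.1 also allows further exclusions of incongruous PK data under a sponsor procedure that is not available to the reader and carries no stated Week 16 limit. This stands in part: the SAP gives no explicit instruction to retain such data. But SAP 5.7.1 points to SAP 5.1.1, not to the protocol, and that section names an end point. Someone following it would apply no window after Week 16.

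Several stronger readings are tempting, and the documents do not support them:
- *That an early late dose destroys all later PK data.* The exclusion covers by-visit analyses only. Population PK has its own plan, and nothing applies the exclusion to it.
- *That the 2-week sentence contradicts the SAP exclusion.* One is an operational dosing rule and the other an analysis rule. A dose can be acceptable in conduct and still be left out of a nominal-time summary.
- *That concentrations are inflated by some factor.* The documents give no half-life and no frequency of late dosing, so the size of any shift in the summaries cannot be estimated.
- *That crossover doses planned 28 days apart could fall 7 days apart.* This needs Week 16 dosed 14 days late (Day 127) and Week 20 seen 7 days early (Day 134). A return to the nominal schedule puts Week 20 on Day 141, an interval of 14 days. It is a stacked extreme and does not bear on the SAP phrase.

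Dropping data from the deviation onward is also a legitimate prespecified convention, applied equally to skipped or incorrect doses. It is not criticised here.

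**Conclusion.** The discrepancy is real and narrow. The SAP window ends at Week 16, the protocol window does not, and the PK exclusion relies on the SAP one. Followed literally, a full dose 8 to 14 days late is screened out through Week 16 and not at Weeks 20, 28, 36 or 44, although the Week 32 and Week 48 samples are planned 4 weeks after the Week 28 and Week 44 doses.

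The consequence is limited to descriptive by-visit PK at those two visits. The efficacy endpoints, type I error and power do not depend on the window. The conclusion assumes that the guselkumab group's later active doses fall at Weeks 20, 28, 36 and 44; the crossover group's weeks are stated. How many participants would be affected cannot be judged from the documents.

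**What to change.** In SAP 5.1.1.1, delete the words that confine the window to the period from baseline to Week 16, so that ±7 days applies to all post-baseline doses as in the protocol. The cross-reference in SAP 5.7.1 then works unchanged. The change should be made before the Week 56 database lock.

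The cost is one phrase and a few more excluded values: a late Week 20 or 28 dose would remove that participant's Week 32 and 48 concentrations from the by-visit summaries, and a late Week 36 or 44 dose the Week 48 value.

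Separately, the sponsor should reconcile two sentences in protocol 6.4, the approximately 2-week dosing sentence and the ±7-day visit-window sentence with its call for sponsor consultation, and state how they combine. This review takes no position on which dosing rule is right.

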5.2. Participant Dispositions

The number of participants screened will be summarized overall.

Disposition will include tabulations, by randomized treatment group, of the number of participants who discontinued study agent administration, the primary reasons for discontinuation of study agent administration, the number of participants who discontinued study participation, and the primary reason for discontinuation of study participation.

Tabulations by randomized treatment group will also be provided for participants who met 1 or more ICE criteria as defined in Section 5.3.2.

Disposition data will be summarized through the study periods that include but are not limited to the following:

1. From Week 0 through Week 16 (Placebo Controlled Period)
2. From Week 0 through Week 48 (Placebo Controlled and Active Treatment Period)
3. From Week 16 through Week 48 (Active Treatment Period)

In addition, participants who were randomized but never treated and participants who were unblinded during the study will be presented in data listings.

5.3. Primary Endpoint(s) Analysis

The proportion of participants who achieve an Investigator's Global Assessment (IGA) score of cleared (0) or minimal (1) at Week 16. The primary endpoint analysis will be compared between the guselkumab treatment and the placebo treatment group and tested at a 2-sided α -level of 0.05.

Composite Strategy

The Composite Strategy assesses the treatment effects not only based on the variable measurements, but also based on intercurrent events (ICE) defined in Section 5.3.2.1.

If a participant met any of the ICEs in categories 1-2, then it will be handled with the composite strategy. Under the composite strategy, participants with the ICE prior to Week 16 will be treated as non-responders for the IGA cleared (0) or minimal (1) response for the primary analysis, regardless of the observed data.

Treatment Policy Strategy

If a participant met the ICE 3, then it will be handled with a treatment policy. Observed value will be used if available. For participants experiencing multiple ICEs, an ICE in categories 1-2 will supersede an ICE in category 3.

5.3.1. Definition of Endpoint(s)

5.3.1.1. Investigator's Global Assessment (IGA)

The Investigator's Global Assessment (IGA) documents the investigator's assessment of the Participant's psoriasis at a given time point. Overall lesions are graded for induration, erythema, and scaling. The patient's psoriasis is assessed as cleared (0), minimal (1), mild (2), moderate (3), or severe (4). Primary efficacy endpoints related to the IGA score is defined below:

IGA cleared or minimal responder

Participants who achieve an IGA score of cleared (0) or minimal (1) will be considered IGA cleared or minimal responders.

5.3.2. Estimand**5.3.2.1. Primary Estimand (Estimand 1)**

The primary endpoint is the proportion of participants achieving an IGA score of 0/1 response at Week 16. This endpoint will be analyzed based on the estimands defined by the following 5 components:

- **Population:** Participants with low body surface area (BSA) moderate plaque psoriasis with special site involvement.
- **Treatment:**
 - Placebo
 - Guselkumab
- **Variable (Endpoints):** The proportion of participants who achieve an Investigator's Global Assessment (IGA) score of cleared (0) or minimal (1) at Week 16. Participants who have intercurrent events (ICEs) 1-2 (defined below) prior to Week 16 will be considered as not achieved for IGA 0/1 response, regardless of the observed data.
- **Intercurrent Events (ICEs):** The following are the ICEs and corresponding strategies for this trial.
 1. Initiated protocol prohibited medications/therapies for psoriasis, except for the following
 - a) If the prohibited medication is a corticosteroid and was used for an indication other than psoriasis and for ≤ 2 weeks (short term use)
 - b) If the prohibited medication is a corticosteroid and the mode of delivery is inhaled, otic, ocular, nasal or other route of mucosal delivery.
 2. Discontinued study intervention due to lack of efficacy (e.g., lack of efficacy or an AE of worsening of psoriasis)
 3. Treatment discontinuation due to reasons other than ICE 2.

ICE categories 1 to 2 will follow the composite strategy, where participants who meet them prior to Week 16 will be considered as nonresponders for IGA cleared (0) or minimal (1) response for the primary analysis, regardless of the observed data. The ICE category 3 will follow the treatment policy strategy, where participants who meet them prior to week 16, will use the observed values. For participants experiencing multiple ICEs, an ICE in categories 1 to 2 will supersede an ICE in category 3.
- **Population level summary:** Difference in proportion of participants who achieve an IGA score of cleared or minimal (IGA 0/1) between guselkumab and placebo at Week 16.

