### **6.8.2. Prohibited Concomitant Medications**

#### **6.8.2.1. Topical Treatments**

All topical therapies, including prescription strength and active ingredient OTC shampoos, that could affect psoriasis or any efficacy evaluations are not permitted at any time during the study. These include, and are not limited to, corticosteroids, coal tar preparations, anthralin, calcipotriene, tazarotene, methoxsalen, pimecrolimus, tacrolimus, traditional ethnic medicines (Taiwanese, Korean, Chinese, etc.), tapinarof, roflumilast, etc.

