### **6.8.3. Concomitant Medications for Conditions Other Than Psoriasis**

Every effort should be made to keep participants on stable concomitant medications. If the medication is temporarily discontinued because of abnormal laboratory values, side effects, concurrent illness, or the performance of a procedure, the change and reason for it should be clearly documented in the participant's medical record.

The use of stable doses of nonsteroidal anti-inflammatory drugs is allowed. However, disease-modifying agents such as MTX, sulfasalazine, or IM gold are prohibited during the study.

The use of corticosteroids for indications other than psoriasis should be limited to situations for which, in the opinion of the treating physician, there are no adequate alternatives. They should be used on a short-term basis, preferably for  $\leq 2$  weeks. Longer-term use of corticosteroids should be discussed with the medical monitor or designee and may require discontinuation of study drug. Inhaled, otic, ocular, nasal, or other routes of mucosal delivery of corticosteroids are allowed throughout the study.

The Sponsor must be notified in advance (or as soon as possible thereafter) of any instances in which prohibited therapies are administered.

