**Intercurrent events (ICEs) and corresponding strategies:**

The following are the ICEs considered for this trial:

1. Initiated protocol prohibited medications/therapies for psoriasis
2. Discontinued study intervention due to efficacy (e.g., lack of efficacy or an AE of worsening of psoriasis)
3. Treatment discontinuation due to reasons other than ICE 2.

ICEs in categories 1 and 2 will be handled with the composite strategy. The composite strategy assesses the treatment effects not only based on the variable measurements, but also based on ICEs. Under the composite strategy, participants with the ICE prior to Week 16 will be treated as non-responders for the IGA score of cleared (0) or minimal (1), regardless of the observed data.

ICE 3 will be handled with a treatment policy. The observed value will be used if available.

For participants experiencing multiple ICEs, an ICE in categories 1 or 2 will supersede an ICE in category 3.

**Population level summary:** The difference in proportion of participants who achieve an IGA score of cleared (0) or minimal (1) between guselkumab and placebo at Week 16.

The analysis of the primary endpoint will be based on the Full Analysis Set. Participants will be analyzed according to the intervention group to which they were randomized regardless of the study intervention they actually received.

Participants with missing data, defined as those who terminated the study prior to the Week 16 visit or participants who have a missing value at the Week 16 visit, will be considered to not have achieved their primary efficacy endpoints.

To compare the guselkumab versus placebo group for the primary endpoint, a 2-sided CMH chi-square test stratified by special site will be used. The study will be considered successful if the test of the primary endpoint is positive at the 0.05 significance level.

Additional sensitivity/supplemental analyses which vary how ICEs (e.g., alternative estimand) are handled and how observed data are used will be specified in the SAP to further address the robustness of treatment effect of an IGA score of cleared (0) or minimal (1) with at least 2-grade improvement from baseline at Week 16.

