5.3.3. Analysis Methods

The primary endpoint will be analyzed at Week 16 DBL based on the primary estimand. If a participant experiences ICE of 1 or 2 prior to Week 16, will be treated as non-responders for, IGA score of cleared (0) or minimal (1) response, for the primary analysis. If a participant experiences ICE of 3 then observed value will be used if available.

This primary analysis will include all data collected up to and including Week 16 for all participants in the primary efficacy analysis set. In these primary efficacy analyses, data from all randomized participants will be analyzed according to their assigned treatment group. The primary endpoint at Week 16 will be summarized for each treatment group.

To address the primary objective, a 2-sided ($\alpha=0.05$) CMH chi-squared test stratified by special site (scalp, face, intertriginous, genital) will be used for the primary endpoint.

Statistical analysis for both primary (Estimand 1) and supplementary estimand (Estimand 2) are the same.

The overall Type I error rate will be controlled at the significance level of 0.05. The study will be considered positive if the guselkumab group is significantly different from the placebo. Primary endpoint will be tested at a 2-sided α -level of 0.05.

If the comparison is positive for the primary endpoint, the testing will continue to the major secondary endpoint.

Participants with ICE categories of 1 or 2 before Week 16 will be considered as non-responders at Week 16. Participants with ICE category of 3 before Week 16, observed data will be utilized in the analysis. After accounting for the ICEs for the primary estimand, participants with the missing data of the primary endpoint at Week 16 will be considered as non-responders.

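### SAP exception (b) to intercurrent event 1 exempts corticosteroids by route alone, without the non-psoriasis limit that exception (a) and protocol 6.8.3 carry

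*SAP*

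**What the plan says.** Protocol 9.4.2 defines ICE 1 as "Initiated protocol prohibited medications/therapies for psoriasis" and lists no exceptions. SAP 5.3.2.1 keeps that stem but adds to it: "Initiated protocol prohibited medications/therapies for psoriasis, except for the following". Two exceptions follow.

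- Exception (a) applies "If the prohibited medication is a corticosteroid and was used for an indication other than psoriasis", and only for use of up to 2 weeks.
- Exception (b) applies "If the prohibited medication is a corticosteroid and the mode of delivery is inhaled, otic, ocular, nasal or other route of mucosal delivery". It sets no limit on indication, duration or site of application.

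The consequence of ICE 1 is in SAP 5.3.3: "Participants with ICE categories of 1 or 2 before Week 16 will be considered as non-responders at Week 16". A participant covered by an exception has no ICE 1, so the observed score is used.

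The protocol deals with corticosteroids in two places. Section 6.8.3, headed "Concomitant Medications for Conditions Other Than Psoriasis", contains the route allowance: "Inhaled, otic, ocular, nasal, or other routes of mucosal delivery of corticosteroids are allowed throughout the study". Section 6.8.2.1 covers topical therapies, names corticosteroids among them, and says those "that could affect psoriasis or any efficacy evaluations are not permitted at any time during the study".

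**The concern.** The composite strategy exists so that a participant who needed another psoriasis treatment is not credited with a response. Exception (b) removes part of that protection. It takes over the route list of protocol 6.8.3 without that section's restriction to other conditions, while exception (a), directly above it, states the restriction.

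A programmer following the text would exempt by route alone. A corticosteroid used against psoriasis and recorded under one of these routes would not trigger non-response, and its effect could be counted as a response to the assigned arm.

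The definition travels. SAP Table 8 uses the same ICE numbering for all 12 major secondary endpoints without restating it. Estimand 2 keeps the components of the primary estimand, so it inherits the gap and cannot serve as a check on it.

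**Working it through.** **1. Does any text restore the limit?** Four places bear on it.

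| Place | Non-psoriasis limit |
|---|---|
| SAP 5.3.2.1, exception (a) | Stated |
| SAP 5.3.2.1, exception (b) | Absent |
| Protocol 6.8.3 (same route list) | In the section heading |
| Protocol 9.4.2, ICE 1 | No exceptions listed |

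No other SAP section restores it. A corticosteroid given by these routes for another condition is already allowed under 6.8.3. It is therefore not a prohibited psoriasis therapy and does not meet the ICE 1 stem. Taken literally, exception (b) has effect mainly where the steroid is prohibited, which includes use for psoriasis.

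**2. Which endpoints are exposed?** The IGA is averaged over all lesions (protocol Appendix 9), and entry requires at least one plaque outside the special sites (inclusion criterion 3). Local treatment of one area would seldom give whole-body IGA 0/1. The sPGA-G scores the genital area alone, and the i-IGA includes the perianal region. These two are the endpoints that local treatment could move.

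**3. Reproduce the plan's power.** Two-sided alpha 0.05, pooled-variance z test, placebo n1 and p1, guselkumab n2 and p2, p̄ = (n1p1 + n2p2)/(n1 + n2):

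power = Φ{ [ (p2 − p1) − 1.96·√(p̄(1 − p̄)(1/n1 + 1/n2)) ] / √(p1(1 − p1)/n1 + p2(1 − p2)/n2) }

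Genital or intertriginous set (SAP Table 4: 25 vs 50, 10% vs 45%):

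- p̄ = (2.5 + 22.5)/75 = 0.333
- the two standard errors are 0.1155 and 0.0925
- power = Φ[(0.35 − 1.96 × 0.1155)/0.0925] = Φ(1.34) = 0.91

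The plan states 90%. For the primary endpoint (100 vs 200, 15% vs 60%) the formula gives more than 99%, as stated.

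**4. Sensitivity, primary endpoint.** The documents give no rate of mucosal-route use for psoriasis, so any shift is an assumption. Raising the placebo rate from 15% to 20%, 25% or 30% lowers the difference from 45 to 40, 35 or 30 points. Power stays above 99% throughout.

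**5. Sensitivity, genital endpoint.** Exact power of the two-sided Pearson chi-square test, guselkumab 45%, with an assumed 0, 1 or 2 exempted placebo participants becoming responders:

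| Extra placebo responders | 25 vs 50: placebo rate, power | 40 vs 80 (assumed): placebo rate, power |
|---|---|---|
| 0 | 10%, 91% | 10%, 99% |
| 1 | 14%, 80% | 12.5%, 97% |
| 2 | 18%, 66% | 15%, 93% |

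The second size is shown because 25 vs 50 is the enrolment target per randomization stratum. SAP Table 6 defines the genital set as everyone with baseline sPGA-G ≥3, including participants with several qualifying sites who were randomized under another site. The set may therefore be larger than 75.

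In the other direction, 1 to 3 extra guselkumab responders out of 50 would raise the difference from 35 to 37, 39 or 41 points.

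**The case against.** The strongest reply is that exception (b) was plainly meant to restate protocol 6.8.3, so non-psoriasis use is implied. That intent is likely. But the limit is written into (a) and not into (b), and a rule that sets responder status should not depend on inferred intent.

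A second reply is that protocol ICE 1 covers only prohibited therapies, so for non-psoriasis use the exemption is already implicit and the SAP is entitled to add detail. This is correct, and it narrows the conflict to use for psoriasis.

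A third reply concerns reach, and most of it stands. A reader might infer that treated genital, perianal or ear disease will now count as a response. The documents do not support that as stated. Of these, only the otic route is named, and the ear is not among the qualifying sites. A cream on genital or perianal skin would naturally be recorded as topical and stay within ICE 1. It escapes only if coded under the residual mucosal category, which neither document defines.

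A reader might also take the fall from 91% to 66% in the table as the expected loss. It is not. It needs two participants who break the protocol, are coded as mucosal, reach sPGA-G 0/1 and do not stop study drug for lack of efficacy (which would be ICE 2), all in a set of the smallest planned size.

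**Conclusion.** The wording gap is real and can be read directly from the text. As written, exception (b) leaves a corticosteroid given for psoriasis by one of the listed routes outside ICE 1, contrary to protocol 6.8.2.1 and 9.4.2.

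Its practical size is small or unknown. The primary comparison is hardly exposed, and its power stays above 99% even under large assumed shifts. The plausible exposure is sPGA-G and i-IGA, conditional on how genital or perianal application is coded. These are seventh and eighth in the fixed sequence, so a miss at sPGA-G would stop formal testing of endpoints 8 to 12.

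A reader might infer that the exception favours guselkumab. The documents do not establish a direction. If such use is commoner on placebo, which is an assumption, the treatment difference shrinks. Use in the guselkumab arm would act the other way.

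**What to change.** In SAP 5.3.2.1:

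1. Add to exception (b) the non-psoriasis indication limit that exception (a) already has.
2. State that topical application to genital, perianal or other skin is not mucosal delivery for the purpose of this rule.
3. State that this one ICE 1 definition applies to Estimands 1-14.
4. Classify each case before the Week 16 lock, blinded to treatment, from the reason-for-use field that protocol 6.8 already requires.

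Do not go further and also exclude any steroid applied to psoriatic skin or mucosa. That could turn non-psoriasis use allowed by 6.8.3 into non-response, and it needs an application-site field that protocol 6.8 does not list.

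The change concerns the analysis rule only. It reconciles the SAP with protocol 6.8.2.1, 6.8.3 and 9.4.2 and takes no position on which treatments should be permitted. It alters no sample size and needs no new data. The cost is a short SAP edit and a blinded review of existing records; the downside is possibly a few more participants counted as non-responders.
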